Data will not be presented masked to the external data monitoring committee.

17b. Circumstances to reveal masking.

It will be considered to reveal the masking of the outcome in the event that any of the participants present at the time of recording for the measurement of the outcome great psychological or emotional affectation by the simulation and the safe container described in the simulation methodology is not enough.

V Methods: data collection, management and analysis.

18. Baseline and outcome data collection plan

Baseline characteristics: the following baseline characteristics of the participants in the first simulation session will be collected: age, sex, personal history of sleep disorders, personal history of mood disorders, hours of weekly care rotation, hours of daily sleep on average, reported simulation training hours, weekly work hours if applicable. On the day of the outcome measurement, the variable hours of sleep the day before the outcome measurement will be recorded. The variables to be registered are discriminated in Annex 5.

These data will be filled out in physical form and will be transcribed in a database in Google documents.

The outcome variables will be carried out electronically and are summarized in Table 8.

Outcome	Measurement	Responsable	
Primary			
Skipping treatment steps	Electronic format in Google	Blind collaborator to the	
	based on video recording.	intervention	
	Secondary		
Crisis resolution time	Electronic format in Google	Blind collaborator to the	
	based on video recording.	intervention	
Time in detection and	Electronic format in Google	Blind collaborator to the	
discrimination of the crisis	based on video recording.	intervention	
Overall score of non-technical	Electronic format in Google	Blind collaborator to the	
skills	based on video recording.	intervention	
Discriminated score between	Electronic format in Google	Blind collaborator to the	
dimensions of non-technical	based on video recording.	intervention	
skills			
Student satisfaction	Electronic version of Format	Self completed by the	
	F-025-08 of the Simulation	Student in an anonymous	
	Center, Faculty of Medicine,	format.	
	University of Antioquia		
Incidence of inadequate crisis	Electronic format in Google	Blind collaborator to the	
management	based on video recording.	intervention	

Table 8 measurement of outcome variables

18b. Plan to promote retention and complete follow-up

The participation, retention and follow-up of the study will be voluntary, based on the explanation of the potential benefits in the participation of the study, such as training in high-fidelity simulation of both interventions, no financial remuneration will be used as a retention strategy.

Since a minimum of three sessions participation on different days is required for high-fidelity simulation training and outcome measurement, a possible participant loss of 20% is considered, which was included in the sample size calculation.

The participant can withdraw from the study at any time they wish, even after randomization, this will be clarified from the beginning of the intervention and follow-up period, in addition it will not have repercussions on any qualification in any of the internship courses to be attended by the competitor.

It will be carried out independently of the possible withdrawals from the study, analysis by intention to treat.

19. Data handling:

After completing the manual forms in their entirety, they will be subjected to quality control during the days of administration of the interventions, avoiding loss of data from the start of the study. After that, the central office of the present investigation located in the Faculty of Medicine of the University of Antioquia will be taken in an opaque and sealed envelope, where an administrative assistant with experience in electronic data management and investigation will enter the information from the formats. manuals to an electronic database that will have two backup copies and to which said assistant will only have access during data collection. Subsequently, they will be presented blinded to the researcher who will carry out the statistical analyzes described in the analysis plan.

20 a. Analysis methods for primary and secondary outcomes.

The baseline characteristics of the participants in both groups will be summarized with measures of frequency and proportions for the qualitative variables. In the case of quantitative variables, measures of central tendency and dispersion, mean and standard deviation or median and interquartile range will be used after performing the Shapiro Wilk normality test.

The analysis of each variable is explained in Table 9, prior to the use of parametric tests, the necessary assumptions will be verified including probability distribution tests, independence of the data and equality of variances according to the case. For the ratio of proportions and mean differences of the groups, in case of non-compliance, non-parametric statistical inference will be made.

To compare the intervention arm: training with non-technical skills and checklists with the control group: training with checklists, the proportion of omission of treatment steps per group will be used as the primary outcome variable.

Alternate hypothesis: the difference in the proportion of omission of treatment steps between the control and intervention group is greater than 10%.

Null hypothesis: the difference in the proportion of omission of treatment steps between the control and intervention group is 10% or less.

Table 9 analysis plan by variable

Outcome	Outcome	Statistical	Estimator	Analysis
	measure	hypothesis		method
Primary outcome: Medical error	Ratioofomissionoftreatmentstepsto totalstepsgroup.	Ha: Pcontrol - P intervention> 10% HO: Pcontrol - Intervention = 10%	Difference in proportions (95% CI)	Chi square test
Overall score on non-technical skills scale	Average Interval per group between 1 to 45	He has: µintervention>µcontrol Ho: µintervention≤ µcontrol	Mean difference (95% Cl)	T Student test.
Ottawa Leadership on Scale	Average Interval per group between 1 and 7	He has: µintervention>µcontrol Ho: µintervention≤ µcontrol	Mean difference (95% CI)	T Student test.
Ottawa scale problem solving	AverageIntervalpergroupbetween 1 and 7	AverageIntervalper groupbetween1 and 7	Mean difference (95% CI)	T Student test.
Situational awareness on the Ottawa scale	AverageIntervalpergroupbetween 1 and 7	Hehas:µintervention>µcontrolHo:µintervention≤µcontrol	Mean difference (95% CI)	T Student test.
Utilization of Ottawa scale resources	Average Interval per group between 1 and 7	He has: µintervention>µcontrol Ho: µintervention≤ µcontrol	Mean difference (95% CI)	T Student test.
Ottawa Scale Communication	Average Interval per group between 1 and 7	He has: µintervention>µcontrol Ho: µintervention≤ µcontrol	Mean difference (95% CI)	T Student test.
Crisis resolution time	Average time in minutes per group	He has: µintervention< µcontrol Ho: µintervention≥ µcontrol	Mean difference (95% CI)	T Student test.
Timeindetectionanddiscrimination ofthe crisis	Average time in minutes per group	He has: µintervention< µcontrol Ho: µintervention≥ µcontrol	Mean difference (95% CI)	T Student test.
Student satisfaction	Difference of excellent assessment proportions in the categories of the format F- 025-08	Ha: Pintervencion> Pcontrol Ho: Pintervencion = Pcontrol	Difference of proportions. (95% CI)	Fisher's Exact Test.

IncidenceofRelativeriskHa: RR ≠ 1improperinadequateHo: RR = 1handlingmanagementintervention /control	Relative Risk (95% CI)	Chi square test.
--	---------------------------	------------------

20b. Additional analysis methods

Other analyzes by subgroups or adjustment of analysis by other variables will not be considered.

20c. Methods for analysis of censored or missing data

In case of censored or lost data, multiple imputation method will be carried out (43).

VI Methods: data monitoring

21a. Composition of the data monitoring committee

The Tecrisis study will have a data monitoring committee external to the research group, which will be made up of the coordinator of the simulation center of the Faculty of Medicine of the University of Antioquia, a clinical simulation teacher from outside the study, and a researcher from the research group. GRIMPA Research in Perioperative Medicine.

21b. Interim Analysis Description

An interim analysis will be carried out with 50% of the participants collected, blind and foreign to the research group, only for adverse events in the case suggested by the data monitoring committee.

22. Damage

Given that it is an educational study that uses the same strategies that are usually used in the training of participants, no adverse events are expected other than a possible emotional affectation due to the high fidelity simulation. The report and management of this will be done according to the institutional protocol of the simulation center of the Faculty of Medicine of the University of Antioquia. However, this study is low risk since the participants are constantly exposed to simulation as a teaching tool and reaching an adequate degree of stress can improve learning even in this scenario.

Other unforeseeable adverse events within this protocol will be reported in case of presenting to the simulation center of the Faculty of Medicine of the University of Antioquia and to the ethics committee of the same institution.

Any non serious adverse event will be recorded and evaluated according to the following characteristics: expected / unexpected, severity, possible cause, management and outcome.

23. Audit

An audit of adherence to the protocol is proposed by the data monitoring committee once a semester, regardless of the percentage of the sample collected.

VII Ethics and dissemination

24. Approval by ethics committee

This protocol and informed consent will be evaluated and submitted for approval by the ethics committee of the Faculty of Medicine of the University of Antioquia.

We consider that it complies with the seven recommendations of the American Medicine Association(44).

1. Social or scientific value: this section is fulfilled since a clinical study is proposed that can improve health results and possibly provide tools or confirm existing tools to reduce medical error due to the omission of treatment crises. In addition to increasing knowledge of non-technical skills and checklists that could improve the satisfaction of students in the medicine program at the University of Antioquia.

2. Scientific validity: the principles and methods including statistical analyzes are proposed based on the recommendations of the Master of Clinical Epidemiology of the University of Antioquia with the aim of resulting in valid and reproducible data.

3. Fair selection of subjects: the selection of the participants does not generate any vulnerability, on the contrary, they could contribute to the training process as medical professionals. Participation in this study does not lead to risks of social stigmatization. In addition, as a matter of justice, it is proposed after recording for the outcome measurement to carry out the two intervention and control training sessions for the two groups.

4. Adequate risk-benefit ratio: given the simulation methodology as a tool for the administration of the intervention and control, based on good judgment, the risks of adverse events are minimized, which are similar to those of any simulation teaching scenario. Among the potential benefits is increasing exposure to medical crisis resolution training with the goal of reducing medical error.

5. Independent review: This protocol has two independent and blind review times. A first moment by two professors of the Master of Clinical Epidemiology at the University of Antioquia and a second moment with two independent pairs.

6. Informed consent: ample and sufficient information will be provided for informed consent in which the interventions, the potential risks, benefits and alternatives are explained.

7. Respect for potential and enrolled participants: this recommendation is met since participants can withdraw at any time from the study without any summative or formative retaliation, privacy of all participants is protected, participants will be informed in case of new information and a constant monitoring of adherence to the protocol will be carried

out. In addition, it is a low-risk study that complies with the recommendations of the World Health Organization for clinical studies in humans. (Four. Five) and with the ethical principles of respect for people, justice and charity manifested in the Declaration of Helsinki and the Belmont Report.

It also complies with the recommendations of the ministry of social protection in Colombia expressed in resolutions 8430 of 1993(46) and 2778 of 2008 of good clinical practices(47).

25. Modifications to the protocol

In the event that there is any modification to this protocol that impacts the conduct of the study, for example, the potential benefit of the interventions in the participants, the objectives, the design, the population or the sample size, a formal correction will be made of the protocol, will be presented to the ethics committee of the University of Antioquia and will be implemented after its approval. For administrative corrections that do not generate changes in the conduct of the study, notification will be made to the ethics committee without formal protocol change.

26. Informed Consent

Informed consent will be obtained from the participants eligible for the present study, from one of the researchers who does not participate in the summative evaluation of the clinical rotations, this in order not to generate possible pressure on the participants, the potential benefits of the two educational interventions and the expected results. A benefit of participating in the study is that it includes three simulation days in addition to the standard undergraduate curriculum training. Possible adverse effects such as emotional impairment will be explained and authorization will also be requested for the use of the data generated from this research in other research protocols. Informed consent can be seen in its entirety in Annex 2.

27. Confidentiality

All the information on paper related to the study will be protected in the simulation center of the Faculty of Medicine of the University of Antioquia, the digital information will be protected in a computer with a password and also one of the researchers will have a backup hard disk with all the information that will also have a login password.

The forms filled out on the Google Docs platform will be protected by institutional mail with a password known by the administrative assistant who files them and the researcher who will analyze them.

The videos made for the outcome measurement will be stored on a computer with a password and also one of the researchers will have a backup hard disk with all the information that will also have a login password, the collaborators who measure the outcome will have access to said videos at the time of such measurement.

28. Declaration of conflict of interest

The present principal investigators do not have any conflict of interest regarding the two interventions that will be carried out.

29. Access to data

During the clinical trial, the collaborators who perform the outcomes will not have access to the data, the main researchers will not have access to the database until the end of the study to avoid loss of blinding.

Researchers will have access to the complete database only at the time of results analysis.

Participants will have access to the personal data of the study once their analysis has been completed, and the database will also be restricted to avoid any information that would allow the patient to be identified.

30. Post-study care

Study participants will continue with their clinical internship rotation with the same academic, evaluative and hourly intensity as students who do not participate in the study, no financial compensation will be made for participation in this clinical trial, nor will pharmacological interventions be performed. or that differ from traditional exposure to the high fidelity simulation, low risk of the presence of adverse effects derived from the intervention is expected.

31. Dissemination policy

31a. Communication plan of the results: it is intended to communicate the results of the present study in different media:

Publication of the main article: the results of this study will be taken to an indexed and homologated journal by Colciencias, even in case of no differences between the groups, there are also no limitations on the part of the financing entities of this study for publication.

Publication of minor article: possible secondary articles derived from this study will be submitted to publication in journals indexed and approved by Colciencias, the authors will be those who design new research questions that can be answered with the possible assembled basis of this study.

31b. Authorship Plan: the authors of the possible publications of this study will be those who meet the criteria required by the different scientific journals, this includes, but is not limited to: patient collection, protocol design, data analysis and final writing. It is not intended to hire professional writers for possible publications, although it is possible for style editing.

31b. Public Protocol Access Plan: the protocol will be published on clinicaltrials.gov and in its full version it will be published on the anesthesiology platform of the University of Antioquia on the teleeducacionmedicina.udea.edu.co page.

VIII Annexes

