12.2d Mean difference between the discriminated score between dimensions of the nontechnical skills of the two groups, measured with the Ottawa global scale based on video recording by an independent evaluator.

Ottawa Global Scale Overview: this scale is free to use for research, it has a validation study in our environment, completed in the publication phase, its psychometric characteristics are summarized in Table 5 (42), the Spanish version can be seen in Annex 6.

Table 5 Ottawa scale psychometric characteristics for HNT

Dimension or item	Internal	Reliability between	Reliability between Reliability re-	
	consistency	ICC evaluators	test	
Overall evaluation	reference	0.641	0.761	
Leadership Skill	0.902	0.634	0.808	0,776
Problem resolution	0.915	0.628	0,779	0.692
Situational awareness	0.930	0.627	0.708	0.576
Use of resources	0.863	0.696	0.70	0.578
Communication skills	0.893	0.597	0.7407	0.872

12.2e Student satisfaction:

This exploratory outcome is chosen because of the importance of the perception of the participants that hypotheses could generate for future research. A search was made of validated and free scales for use without finding any that meets these requirements for high-fidelity simulation, therefore, the training satisfaction assessment format of the simulation center of the Faculty of Medicine of the University of Antioquia, format F-025-08 (see annex 7).

12.2f Incidence of inadequate crisis management:

Difference in incidence of inappropriate management rating, this dichotomous rating will be performed by the blind evaluator of the outcomes, taking into account the treatment actions considered minimal by the researchers based on the different clinical practice guidelines, these are those specific to management by crisis, it will be classified as adequate management if it is met, inadequate management otherwise, according to table 6.

Air embolism	 Stop the air intake site by applying irrigation Start dobutamine or norepinephrine if hypotension in less than 2 minutes Position in lateral decubitus on the affected side before 10 minutes
Anaphylaxis	 Stop infusions Apply Adrenaline IM or IV in less than 2 minutes Apply infusion epinephrine in case of non-response of 1 to 4 micrograms / minute
Unstable Bradycardia	 Apply atropine 0.5mg IV repeat up to 3mg total dose If bradycardia persists use transcutaneous pacemaker

Table 6. Minimum	treatment	actions for	crisis	resolution.
	cicacificiti		011515	resonation.

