The proportion of treatment steps and not the incidence of medical error is taken as the unit of analysis, the reason for this is the high incidence of medical error that can even manifest itself with more than one error due to crisis, therefore, if used the incidence of the event would decrease the sample size.

Based on the study by Arraiga et al., The proportion of missed treatment steps in the expected control group is 26% and we consider a further 10% reduction in the intervention group to be clinically important. A minimum of 10% additional reduction in omitting treatment steps is decided because it is the approximate effect size of the other dimensions of non-technical skills other than resource management, a dimension that includes the use of checklists. It also establishes power of 90% and alpha of 0.05.

The sample calculation is then carried out in the analysis unit omitting treatment steps according to the formula:

$$n = \frac{\left[Z_{*} * \sqrt{2p(1-p)} + Z_{p} * \sqrt{p_{1}(1-p_{1}) + p_{2}(1-p_{2})}\right]^{2}}{(p_{1}-p_{2})}$$

With the statistical program R version 4.0.0 epiR statistical package, with the following code:

> library (epiR)

> epi.propsize (treat = 0.16, control = 0.26, n = NA, power = 0.9, design = 1, sided.test = 2, conf.level = 0.95)

We found a sample size of 492 treatment actions per arm, which corresponds to 984 in total, and with an estimate of student losses of 20%, we found the total of 1,180 treatment actions; Since 21 treatment steps are evaluated in each team, we obtain a total of 56 final semester medical students, 28 in each arm.

15. Recruitment

In order to complete the calculated sample size, the following recruitment strategies will be carried out:

- Explanation of the project at least once per internship cohort with the whole group.
- Request for participation on day 1 of the anesthesiology rotation in boarding school and the care rotation of the critically ill patient.

Table 8. Monthly evaluation of the monitoring status

Recruitment month	one	2	3	4	5	6	7	8
Current current income								
Income to date								
Income goal to date								
Real less projected								
Success ratio								
Projected final income								
Final deficit or excess								

IV Methods: allocation of interventions

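### Section 20a answers failed independence with unnamed non-parametric inference, which does not correct for 21 steps clustered within each randomised student

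*Combined protocol and SAP*

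**What the plan says.** Section 20a states that, before parametric tests are used, "the necessary assumptions will be verified including probability distribution tests, independence of the data and equality of variances according to the case". For both proportions and mean differences it then gives a single remedy: "in case of non-compliance, non-parametric statistical inference will be made". It names no non-parametric test, no threshold for failing a check, no unit of analysis and no replacement estimator. Section 20b rules out adjusted analyses.

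Section 14 fixes the unit for the primary outcome: "The proportion of treatment steps and not the incidence of medical error is taken as the unit of analysis". It counts 21 steps per student and sets the design argument of the sample-size call to 1. Section 12.1 asserts that the evaluations are independent of one another. Section 16a randomises individual students. Table 9 compares omitted steps by chi-square.

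For crisis resolution time, detection time and Ottawa scores, Table 9 gives a group average, a Student t-test and a mean difference with 95% CI. Section 12.2f defines the remaining video outcome as "Difference in incidence of inappropriate management rating, this dichotomous rating will be performed by the blind evaluator", judged crisis by crisis against Table 6 and tested by chi-square. None of these entries says how a student's three crises become one value, or whether they do.

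**The concern.** Independence is the one assumption that need not be tested, because the design settles it. Steps performed by the same student in the same recordings will tend to succeed or fail together. A rule that checks independence and then moves to a rank or Fisher test replaces one test that needs independent observations with another. The p-value and interval for the primary outcome would still treat 21 correlated steps as 21 separate pieces of evidence, so a false claim of benefit becomes more likely than the nominal 5%.

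The second issue is smaller. If a pre-test fails for a time or a score, Table 9 promises a mean difference but section 20a does not say what would be reported in its place. What is estimated could then depend on the data.

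**Working it through.** **Inputs.**
- From section 14: "It also establishes power of 90% and alpha of 0.05"; rates "treat = 0.16, control = 0.26"; "sided.test = 2, conf.level = 0.95"; design argument 1, which amounts to ICC = 0; 28 students per arm.
- Steps per student: 3 crises × 7 steps = 21, which agrees with section 14. Steps per arm: 28 × 21 = 588.
- ICC: not given in the documents. The ranges below are assumptions.

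The stated inputs give 347 steps per arm by the usual two-proportion formula, not the plan's 492. That is a separate matter and does not enter the type I error below.

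**Step 1: primary outcome, step as unit.** Design effect DE = 1 + (21 − 1) × ICC. A nominal two-sided 5% test that ignores it has type I error 2 × [1 − Φ(1.96/√DE)]. At ICC 0.05, for example, DE = 2.0, 1.96/√2.0 = 1.386, and the error is 16.6%. This was checked with 4,000 simulated beta-binomial null trials per ICC (28 students per arm, 21 steps, common omission rate 0.21). The null is no difference between arms, which is what an ordinary chi-square tests.

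| Assumed ICC | 0.02 | 0.05 | 0.10 | 0.20 |
|---|---|---|---|---|
| DE | 1.4 | 2.0 | 3.0 | 5.0 |
| Formula | 9.8% | 16.6% | 25.8% | 38.1% |
| Chi-square on steps | 9.9% | 17.3% | 26.0% | 37.8% |
| Mann-Whitney on steps | 9.9% | 17.3% | 26.0% | 37.8% |
| Fisher on steps | 9.0% | 15.8% | 24.3% | 36.3% |
| t-test on student proportions | 5.2% | 5.1% | 4.9% | 4.3% |
| Mann-Whitney on student proportions | 5.0% | 5.1% | 4.5% | 4.7% |

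A repeat simulation at ICC 0.02, 0.05 and 0.10 gave about 10%, 18% and 25% for chi-square and 9%, 16% and 23% for Fisher. Changing the test at step level repairs nothing; changing the unit does.

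**Step 2: outcomes with one value per crisis.** If the three crises are pooled (84 values per arm), DE = 1 + 2 × ICC. At assumed ICC 0.1, 0.3 and 0.5, DE is 1.2, 1.6 and 2.0.

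| Assumed ICC | 0.1 | 0.3 | 0.5 |
|---|---|---|---|
| Formula | 7.4% | 12.1% | 16.6% |
| Pooled t-test | 7.3% | 12.9% | 16.6% |
| Pooled Mann-Whitney | 7.3% | 12.3% | 16.2% |
| Mann-Whitney on student means | 4.8% | 4.9% | 4.3% |

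Welch on student means gave 4.9–5.5% across runs. For pooled inadequate management, at an assumed rate of 30%, chi-square gave 7.3%, 12.9% and 17.1%, and Fisher 4.9%, 10.4% and 13.9%.

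**Step 3: the pre-test on its own.** With one independent value per student, the two-stage rule (Shapiro-Wilk and Levene, then t or Mann-Whitney) had type I error 4.6–5.0% for normal, exponential, lognormal and 1–7 scores. With unequal variances it was 5.6% (SD ratio 2) and 6.5% (SD ratio 3) at 28 v 28. It was 8.4% (SD ratio 3) at 28 v 20 with the larger SD in the smaller arm. Welch stayed at 4.9–5.1%.

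**The case against.** Four points can be made for the plan.

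- **The fallback is unnamed, so it is not necessarily invalid.** A permutation test by student or a cluster bootstrap is non-parametric, respects the design and can keep the mean difference. This is true. The documents therefore do not show that the Table 9 estimator would be dropped; they leave it open. But nothing points to such a method, and the usual tests fail here.
- **Pooling is not stated for the secondary outcomes.** Table 9 speaks of group averages, and Annex 5 lists one variable per outcome with no crisis index, which fits one value per student. This stands. A reader might infer that independence fails for every video outcome, but the documents support that only for the step-level primary outcome. Annex 5 also lists the omission rate as a continuous percentage, which hints at a student-level value, but it conflicts with section 14 and with the chi-square in Table 9.
- **The inflation is not caused by pre-testing.** This stands. Pooled t and pooled Mann-Whitney are equally affected, so deleting the pre-test without fixing the unit would cure nothing.
- **Frequent switching is not shown.** A reader might infer that skewed, capped times will fail a normality test more often than not. With lognormal times (log-SD 0.5, capped at 1.6 times the median), Shapiro-Wilk rejects in about 60% of samples of 28 single times. On 28 student means the figure falls to about 4–10%. The documents give neither the spread nor the cap. The test mentioned in "after performing the Shapiro Wilk normality test" governs the description of baseline characteristics, not the choice of outcome test. No switching frequency can be claimed.

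**Conclusion.** The rule is wrong as written for the primary outcome. It treats as testable an assumption that the design already breaks, and its remedy, read as the usual rank or Fisher tests, leaves the error in place. The size depends on an ICC that the documents do not give: about 10%, 17% and 25–26% for chi-square or Mann-Whitney, and 9%, 16% and 23–24% for Fisher, at 0.02, 0.05 and 0.10. The direction is the same for chi-square and Mann-Whitney at any positive ICC.

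For times, Ottawa scores and inadequate management the finding is conditional. If crises are pooled, t and Mann-Whitney are both inflated to about 7%, 11–13% and 16–17% at ICC 0.1, 0.3 and 0.5. If crises are averaged per student, both are valid. The pre-test switch is a lesser fault: it moves the error rate little unless variances differ, but it leaves the reported effect measure undefined.

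**What to change.** In section 20a and Table 9:

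- Remove independence from the assumption checks and drop the data-driven switch.
- State that the student is the unit of analysis for every video outcome, and withdraw the statement in section 12.1 that evaluations are independent.
- For times and Ottawa scores, prespecify a Welch t-test on each student's mean over three crises, with the mean difference and 95% CI.
- For omitted steps and inadequate management, prespecify a student-level proportion or a model clustered by student.
- Name a student-level permutation test or bootstrap as the sensitivity analysis.

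This changes wording only and uses the same data. There is a slight loss of efficiency if distributions are extreme. For the primary outcome, intervals widen by about √DE: √1.4 = 1.18, √2.0 = 1.41 and √3.0 = 1.73 times at ICC 0.02, 0.05 and 0.10. That widening is the true uncertainty.
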